Additionally, clients who are not mentally fit to understand the consenting or study procedures, as well as clients who speak neither English nor Luganda (the local language spoken by the majority of people in and around Kampala) were excluded. As both intervention groups rely on the receipt of text messages, clients who don't own a cell phone or have access to one will also be excluded.

Participation in another adherence study as well as non-ability or non-desire to use MEMS caps regularly throughout the course of the study will also be a basis for exclusion. Consequently, if the baseline MEMS reading suggests that participants opened their pill bottle less than 30% of days, and if that was not a consequence of low adherence, then the participant will be given a transport refund and will be unenrolled from the study. Finally, clients coming outside regular clinic working hours will be excluded.

Randomization and Allocation

Participants will be randomly assigned to either one of the treatment arms (T1 = *Messages*; T2 = *Incentives*) or the control arm after consenting but will only be informed of their assignment after the baseline survey is over to minimize any potential influence of the assignment on the baseline survey responses. The distribution ratios for the randomization will be 1:1:1 and the assignment will be carried out through a computer-generated randomization component built into the baseline survey administration software, called Questionnaire Development System. The random assignment (to either the control group or one of the two intervention arms) will be revealed at the end of the baseline survey to both the participant and the study coordinator, who will therefore not know the respondent's treatment assignment during the survey. Given the

nature of the intervention, neither the interviewers nor the participants can be blinded to the treatment status. However, the data analyst who will conduct the impact analysis will be blinded to treatment assignment.

Procedures

Interventions

The pilot will include a control arm, along with two intervention arms – *Messages* (T1) and *Incentives* (T2).

Control Group: Usual Care

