MEMS-data will be collected continuously over the course of the three-month intervention period allowing for mean adherence assessment during the intervention period. Specifically, the number of pill bottle openings detected by the MEMS cap will be used as a measure of each participant's pills taken per day. Mean adherence will then be calculated as the number of pills taken per day during the intervention period, divided by the number of pills prescribed during the intervention for a given participant (i.e., # of actual bottle openings / # of prescribed bottle openings). This mean adherence measure will be capped at 100%, meaning that any pill bottle openings over the participants' number of prescribed daily pills will be ignored. In this way, the mean adherence measure will range from 0 to 100 and will be calculated for each participant on each day of the intervention period. Only one of the daily ART medication doses will be used to calculate the primary mean adherence variable. Both the mean adherence over the three-month intervention and a monthly measure of mean adherence will be calculated and analyzed.

Primary Outcome 2: Electronically measured mean medication adherence post-intervention

Post-intervention, MEMS data will be collected continuously for six months to investigate post-intervention mean ART adherence ('persistence'). The calculation of this outcome is the same as that of *Outcome 1* except for the timeline over which the data will be collected and analyzed.

Primary Outcome 3: Routinization of ART adherence during intervention

In addition to *Outcomes 1 and 2*, a novel measure of routine adherence will be assessed during the intervention period. The novelty of the measure is in that it is explicitly based on the temporal pattern of pill-taking. The measure will be calculated as the fraction of scheduled pills taken within a two-hour window (+/- one hour) around the typical time that participants report completing their existing routine behavior that anchors their pill-taking. This measure provides an objective way for determining the behavioral automaticity of pill-taking, and will be calculated as the mean of all prescribed pills taken around participants' anchor time over the three-month intervention.

Primary Outcome 4: Routinization of ART adherence post-intervention

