Feasibility and acceptability will be analyzed using summary statistics derived directly from our self-reported measures. To estimate preliminary efficacy, statistical analyses comparing group-level differences in the secondary and tertiary outcome measures will be performed. An Analysis of Covariance framework will be used to test for group differences in each secondary and tertiary outcome, controlling for the participant characteristics that are found to differentiate the groups at baseline. For analyses of dichotomous variables, such as viral suppression, a non-parametric McNemar's test and an analogous multiple logistic regression will be used to control for covariates to assess group differences. In addition to static comparisons of group means for each outcome at three-month intervals, the longitudinal nature of the data will be leveraged by using repeated measures and time-series techniques. Specifically, a linear mixed model with repeated observations will be fit using maximum likelihood through 'xtmixed' in the

software package Stata to study group-level temporal dynamics in daily measures of the primary and secondary outcomes.

Sample and Effect-size Estimation

We will recruit a total of 150 participants and will assume a 90% retention rate through the 9-month study period. This is a conservative estimate of attrition, as previous research in the same clinic and with a similar population observed only 6% attrition over 12-month study periods [44,48]. Given the study objectives of establishing acceptability, feasibility, and preliminary effectiveness, the targeted sample size may not have the power to detect many of the effects that would be clinically significant. Nonetheless, effect size calculations associated with 80% power (2-tailed test) with regard to the primary outcomes at month nine have been carried out. A recent study conducted at Mildmay suggested that mean ART adherence rates are ~ 75% (SD = 20) as measured by MEMS caps [44]. Using these parameters as estimates of adherence for the control group, and 10% attrition at month nine, a sample size of 150 will provide sufficient power to detect a 9% difference in mean adherence between the pooled intervention groups and the control group (effect size = .47), and a roughly 11% difference in mean adherence between the two intervention groups. This translates to the study being able to detect medium effect sizes.

Qualitative Analysis

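### The ANCOVA for the bounded adherence outcomes keeps its default single residual variance; if spread differs by arm, some intervals will have modestly wrong width, which HC3 standard errors would correct cheaply

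*Combined protocol and SAP*

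**What the plan says.** Under Statistical Methods and Analyses, "An Analysis of Covariance framework will be used to test for group differences in each secondary and tertiary outcome", adjusted for characteristics found to differ between the groups at baseline. Nothing is said there about equal or unequal residual variances, robust standard errors, or a model for bounded data. The only sentence on standard errors is under Handling Missing Data and Attrition. It concerns nonresponse weights, which are built only if dropout is found not to be random.

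The outcomes at issue are bounded. For Primary Outcome 1 the protocol states "This mean adherence measure will be capped at 100" (per cent), and Primary Outcome 2 is calculated in the same way. For Primary Outcome 3, with Primary Outcome 4 following it, "The measure will be calculated as the fraction of scheduled pills taken within a two-hour window (+/- one hour" either side of the reported anchor time).

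Sample and Effect-size Estimation takes, for control, "mean ART adherence rates are ~ 75% (SD = 20) as measured by MEMS caps". No SD is given for either intervention arm, and no mean or SD for routinization.

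The labels do not match. The ANCOVA sentence names secondary and tertiary outcomes, while the bounded measures are labelled primary. The two listed secondary outcomes (retention in care and viral suppression) are indicators, dichotomous variables are assigned to other methods, and no tertiary outcome is listed. Read literally, ANCOVA would have no listed outcome to analyse.

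**The concern.** Classical ANCOVA estimates one error variance across all arms and uses it for every contrast. With a control mean of 75 and SD of 20, one SD above the mean is already 95, so an intervention that moves participants toward the ceiling may well reduce the spread in its arm. Control would then have the largest variance and, in the pooled comparison, half the sample of its comparator (45 against 90). A large variance in the smaller group is the case in which a pooled-variance standard error is too small. Between two arms that are both compressed, it is too large.

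What is at stake is the width of the reported intervals. The protocol (Dissemination and Future Directions) says the findings will feed the design of a larger trial, so those intervals will be used.

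**Working it through.** **Inputs from the protocol.** "The distribution ratios for the randomization will be 1:1:1"; "We will recruit a total of 150 participants and will assume a 90% retention rate through the 9-month study period". That gives 150 × 0.90 = 135 analysed, or 45 per arm if attrition is equal. Control mean 75, SD 20.

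**The plan's own figure.** The protocol reports "effect size calculations associated with 80% power (2-tailed test") and gives "a 9% difference in mean adherence between the pooled intervention groups and the control group (effect size = .47"). Alpha is not stated; I assume 0.05. Detectable difference = (1.960 + 0.842) × 20 × √(1/45 + 1/90) = 10.2 points, d = 0.51. The stated 9 points and 0.47 are not reproduced. That is a separate matter. Here 9 points serves only as the planned effect.

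**Standard errors, n = 45 per arm, no covariate.** With contrast weights c:
- Model: SE = √(s_p² × Σc² / n), where s_p² = (s_C² + s_1² + s_2²)/3
- True: SE = √(Σ c² s² / n), using each arm's own s²
- Coverage ≈ 2Φ(1.96 × model/true) − 1

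**Assumed intervention SDs.** Beta distribution with constant precision: 0.75 × 0.25/0.04 − 1 = 3.69, so SD = 100 × √(m(1 − m)/4.69) for a mean m expressed as a proportion. This gives 16.9 at 84, 19.0 at 78.5, 14.2 at 89.5, 13.9 at 90 and 10.1 at 95.

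**Worked case, means 75/84/84 (control/Messages/Incentives).** s_p² = (400 + 286.7 + 286.7)/3 = 324.5.
- Pooled vs control: model √(324.5 × 1.5/45) = 3.29; true √((400 + 0.25 × 573.4)/45) = 3.47; ratio 0.946.
- Incentives vs Messages: model √(324.5 × 2/45) = 3.80; true √(573.4/45) = 3.57; ratio 1.064.

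**Ratio of model to true SE (approximate coverage)**

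| Means C/M/I | SDs | Pooled vs C | M vs C | I vs C | I vs M |
|---|---|---|---|---|---|
| 75/75/75 | 20/20/20 | 1.00 (95.0%) | 1.00 (95.0%) | 1.00 (95.0%) | 1.00 (95.0%) |
| 75/84/84 | 20/16.9/16.9 | 0.946 (93.6%) | 0.972 (94.3%) | 0.972 (94.3%) | 1.064 (96.3%) |
| 75/78.5/89.5 | 20/19.0/14.2 | 0.943 (93.5%) | 0.918 (92.8%) | 1.033 (95.7%) | 1.069 (96.4%) |
| 75/90/90 | 20/13.9/13.9 | 0.889 (91.9%) | 0.940 (93.4%) | 0.940 (93.4%) | 1.167 (97.8%) |
| 75/84/95 | 20/16.9/10.1 | 0.890 (91.9%) | 0.875 (91.4%) | 1.024 (95.5%) | 1.164 (97.7%) |
| Spread grows | 20/24/24 | 1.062 (96.3%) | 1.030 (95.6%) | 1.030 (95.6%) | 0.948 (93.7%) |
| Routinization 30/45/45 (assumed) | 21.2/23.0/23.0 | 1.028 (95.6%) | 1.014 (95.3%) | 1.014 (95.3%) | 0.974 (94.4%) |

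Incentives vs control is too narrow only if 2s_1² < s_C² + s_2². At 75/78.5/89.5, 2 × 360.0 = 720 exceeds 400 + 200.5 = 600.5, so that interval is slightly too wide.

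**Simulated ANCOVA with a covariate.** Beta outcomes, baseline covariate with latent correlation 0.6 (assumed), 45 per arm, 5,000 trials per scenario; Monte Carlo SE √(0.95 × 0.05/5000) = 0.3 points. Coverage, classical then HC3:
- 75/84/84: pooled vs control 93.4%, 95.0%; Incentives vs Messages 96.4%, 95.5%.
- 75/78.5/89.5: Messages vs control 93.0%, 95.3%; pooled vs control 93.0%, 94.4%; Incentives vs control 95.2% (classical).
- 75/90/90: pooled vs control 91.9%, 94.7%; Incentives vs Messages 97.3%, 94.9%.
- No effect: 94.8-95.6%, 94.9-95.9%.

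A separate run of 6,000 trials gave 93.8% vs 95.3% for pooled vs control at 75/84/84 and 92.1% vs 95.1% at 75/90/90.

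**The case against.** The strongest reply is that compression is assumed, not implied. A reader might infer that a mean capped at 100 cannot rise from 75 unless the spread falls. That is wrong: the largest possible SD of a 0-100 variable is √(m(100 − m)), which is 36.7 at mean 84, 30.0 at 90 and 21.8 at 95, so an SD of 20 remains possible at all of them. A mix of responders and non-responders could even widen the spread. Routinization counts only pills taken near the anchor time and may sit mid-scale. This stands, and it limits the directional claims to the compressed case. It does not count against HC3, which does not depend on the direction.

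A reader might also infer that every interval against control is too narrow. The protocol expects Incentives to do better than Messages after the intervention, and under such a graded effect Incentives vs control comes out about right or slightly too wide.

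The text does not prescribe a common variance. It is silent, an ANCOVA framework is compatible with HC3, and analyses with nonresponse weights might use other standard errors. The fair statement is therefore that the default is not relaxed. The label mismatch is also real: the point needs the reading that ANCOVA covers the outcomes labelled primary. That is an inference, although otherwise ANCOVA has no listed outcome.

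Finally, this is a pilot that concedes limited power, and a coverage error of about one point at the planned effect would hardly decide whether a larger trial goes ahead. That stands, and it sets the priority.

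**Conclusion.** The point holds in a limited, conditional form. If the interventions reduce spread on the capped outcomes, the default analysis gives intervals that are modestly too narrow for pooled vs control and Messages vs control. Coverage falls below 92% for Messages vs control (91.4%) only in the most extreme row of the table, where Incentives gains 20 points. The Incentives-vs-Messages interval is conservative.

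The sizes rest on the beta model with constant precision, 45 analysed per arm, alpha 0.05 and, in the simulations, a covariate correlation of 0.6. None of these except the 45 follows from the protocol.

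A reader might infer that the trial's false-positive rate is inflated in general. It is not: with no effect in any arm the variances are equal and type I error is about 5%. The linear mixed model on daily measures was not examined here.

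This is a low-priority improvement, worth making because it costs almost nothing and the protocol describes the analyses as still ongoing.

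**What to change.** Keep the ANCOVA point estimates and state that every arm contrast on mean adherence and routinization uses heteroscedasticity-consistent (HC3) standard errors. In the same edit, correct the ANCOVA sentence so that it names these outcomes, which are labelled primary, in place of secondary and tertiary outcomes.

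The cost is one option in the regression command and one revised sentence; no data collection or point estimate changes. The downside is that intervals become very slightly wider when the variances are in fact equal: simulated coverage with no effect was 94.9-95.9% with HC3 against 94.8-95.6% without.

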A daily list of expected clients will be generated from the master list for the study coordinators to locate those deemed eligible and who are due for a clinic visit. Once a client is located, a pre-baseline visit will be initiated with the study coordinator approaching the client and inquiring about their interest in participating in an ongoing study. On confirming interest, clients will be taken to a separate study room to verify their eligibility, and to receive their consent to participate. Consented participants will be given a medication event management system (MEMS) cap and instructed to store one of their HIV medications in a pill bottle with the MEMS cap attached. Additionally, they will be given a study appointment after approximately one month of this initial visit for adherence data retrieval and baseline survey administration. The first month of adherence data will be used as a baseline and the intervention will not begin before this follow-up visit.

Inclusion Criteria

The study sample will consist of male and female clients aged 18 and older who have started ART at Mildmay within the preceding three months. Treatment initiation is an important eligibility criterion given the conceptual framework of the pilot, which suggests that habit formation during initiation is a key driver for sustained ART adherence over time. Based on electronic records

data from Mildmay, each month at least 100-150 clients with these characteristics begin treatment at the hospital (for a total of 1,758 in 2018); therefore, a large pool of potentially eligible clients will be available for recruitment. Given the nature of the intervention, inclusion will also require participants to own, or have access to a phone at least five days a week throughout the duration of the intervention, while being willing to receive text messages throughout the intervention period.

Exclusion Criteria

Children under the age of 18 were excluded for two reasons: 1) the pediatric clinic is separate from the main recruitment site (which primarily caters to adult clients), and 2) the intervention might require alteration to account for the specific needs of children and adolescents.

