Participants assigned to this arm will receive care as usual, including the adherence support mechanisms that are part of usual care practices. At recruitment, participant will be educated about the importance of pill-taking using a leaflet that details information on how to establish healthy pill-taking routines. Participants will then be asked to select one of the following three pill-taking anchors: getting dressed in the morning, eating a meal (breakfast) in the morning, or eating dinner in the evening, which will also be described in a habit leaflet, and they will be asked to specify the time at which their anchor typically occurs. Once selected, participants will be asked to continue using their MEMS caps and to bring the caps during the next visit.

During each of the subsequent study visits, scheduled roughly one month apart during the intervention period and 1-3 months apart subsequently, participants will be asked a short questionnaire inquiring about changes in their ART adherence behavior, including any changes in location, times, and social activities surrounding their pill-taking behavior and their ART adherence habit strength. They will also be asked about any clinical changes to their ART regimen, as well as about their daily MEMS cap usage. This is because pill-pocketing (dispensing of more than one dose in a given bottle opening event) is a common phenomenon among the population, with 15% of a previous study sample reporting pocketing [48]. If participants indicate pocketing, the study coordinator will work with the participant to find another solution to avoid pocketing and continue using their MEMS cap, and we will adjust for their pocketing in our assessment of their adherence outcomes. Finally, participants will be asked about any changes to their contact information or addresses, and updates will be noted in the contacts data.

The study coordinator will then download the readings from the MEMS cap, inquire about the participants' next visit, and remind them to continue taking their pills on time. This procedure will be carried out throughout the intervention and post-intervention periods.

Treatment Group 1: Messages Group

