The fourth outcome will be calculated using the same procedures as *Outcome 3*. However, the data from which the measure will be assessed will be collected during the post-intervention period.

The team will also assess two secondary efficacy measures, as described below:

Secondary Outcome 1: Retention in care

Retention in care is an important metric of treatment adherence. Failure to remain in care is a commonly observed problem for treatment initiators. To assess how well participants will continue to remain in care, Mildmay electronic records will be used to evaluate the number of study participants who fail to observe their regularly scheduled clinic visits. Participants who don't make any clinic visits for six months or more will be considered lost to follow up. The study coordinator will call them using the tracking information collected for the study to inquire about their reason for stopping care at the Mildmay clinic. This outcome will be measured as an indicator of whether the participants are still active clients at the clinic at the end of the nine-month study.

Secondary Outcome 2: Viral Suppression

HIV RNA (viral load) is our final outcome measure. According to the AIDS Clinical Trials Group, virological failure is defined as a confirmed viral load > 200 copies/mL. Below this level, the viral load is considered undetectable. Importantly, this is a reliable biological measure of ART adherence, since strong adherence leads to lower viral load. Given the intervention design, viral load will be an important complementary measure of adherence. The analysis will examine the intervention effects on the likelihood of being virally suppressed at the end of the nine-month study period.

Data Analysis

[Statistical Methods and Analyses](#)

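### Covariates are chosen by observed baseline imbalance under an unnamed screen, and the baseline month of MEMS adherence enters no stated model for the four primary outcomes

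*Combined protocol and SAP*

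**What the plan says.** **The covariate rule.** Under Statistical Methods and Analyses, ANCOVA is the method chosen to "test for group differences in each secondary and tertiary outcome". The rule for its covariates is given only as "controlling for the participant characteristics that are found to differentiate the groups at baseline". No test, cut-off or candidate list is given. A linear mixed model is then fitted "to study group-level temporal dynamics in daily measures of the primary and secondary outcomes". Its covariates are not listed, and nothing says whether baseline days count as responses.

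**The outcome labels.** The Outcomes section defines four primary efficacy outcomes: mean adherence and on-time adherence, each during and after the intervention. It then says "The team will also assess two secondary efficacy measures, as described below", namely retention in care and viral suppression. No tertiary outcome is defined. Survey measures may be meant, so it is unclear whether the ANCOVA reaches the primary outcomes at all.

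**The baseline month.** Sampling Strategy says "The first month of adherence data will be used as a baseline and the intervention will not begin before this follow-up visit". The only specific use given is the enrolment check under Exclusion Criteria, which applies "if the baseline MEMS reading suggests that participants opened their pill bottle less than 30% of days" and low adherence is not the explanation.

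**Related commitments.** Comparison to prior work puts age and sex in the impact analysis; the methods section does not repeat this. Randomization and Allocation says "the data analyst who will conduct the impact analysis will be blinded to treatment assignment".

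**The concern.** Under randomisation, observed baseline differences arise by chance. A covariate earns its place by predicting the outcome, not by happening to be imbalanced. Adherence recorded by the same cap in the same person a few weeks earlier is a likely predictor of later adherence, and it has already been collected. Under the stated rule it enters only if it passes a screen that nobody has named.

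What is at stake is precision. Sample and Effect-size Estimation already concedes limited power, and Dissemination and Future Directions says the results will feed the design of a larger trial. An open choice among several covariates also leaves the analyst discretion. Blinding limits result-driven choice, but it neither fixes the covariate set nor recovers the lost precision.

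**Working it through.** **Inputs from Sample and Effect-size Estimation and the 1:1:1 allocation.** 150 recruited with 10% attrition leaves 135, or 45 per arm (45 control against 90 pooled). Control mean is 75, SD 20, with 80% power and a two-tailed test.

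**Assumed.** Alpha is 0.05. The correlation r between baseline-month and follow-up mean adherence is 0.3, 0.5 or 0.7.

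**The plan's own figure.** Detectable difference = SD × (1.960 + 0.842) × √(1/n₁ + 1/n₂) = 20 × 2.8016 × √(1/45 + 1/90) = 20 × 2.8016 × 0.1826 = 10.2 points (effect size 0.51). The plan states 9 points and 0.47, so its figure is not reproduced from these inputs. That is a separate matter, and nothing below depends on it.

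**Effect of fixed adjustment.** Replace SD by SD × √(1 − r²):

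- r = 0.3: 10.23 × 0.954 = 9.8 points
- r = 0.5: 10.23 × 0.866 = 8.9 points
- r = 0.7: 10.23 × 0.714 = 7.3 points

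**Effect of the screen.** Three-arm simulation, 3 × 45, bivariate-normal baseline and follow-up, contrast of control against the mean of the two intervention arms, true difference 9 points, 200,000 runs per cell. Standardized-difference screens use the largest pairwise value.

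| Rule | Baseline adherence selected | Power, r=0.3 | r=0.5 | r=0.7 |
|---|---|---|---|---|
| Never adjusted | – | 0.689 | 0.688 | 0.686 |
| ANOVA p<0.05 | 5.0% | 0.691 | 0.696 | 0.703 |
| ANOVA p<0.10 | 10.0% | 0.693 | 0.703 | 0.718 |
| Any pairwise p<0.05 | 12.2% | 0.694 | 0.706 | 0.724 |
| Standardized difference 0.25 | 46.6% | 0.707 | 0.748 | 0.815 |
| Standardized difference 0.2 | 61.2% | 0.712 | 0.764 | 0.849 |
| Standardized difference 0.1 | 88.4% | 0.721 | 0.792 | 0.905 |
| Always adjusted | 100% | 0.725 | 0.804 | 0.927 |

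Share of the gain lost = 1 − (rule − never)/(always − never). At r = 0.5:

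- p<0.05 screen: 1 − 0.008/0.116 = 93%
- cut-off 0.1: 1 − 0.104/0.116 = 10%

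Over all three correlations the loss is 84–94% for the significance tests, 46–50% for cut-off 0.25, 32–36% for 0.2 and 9–11% for 0.1.

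**Type I error.** With one covariate and a fixed screen it is 0.032–0.049 over the six screens, and 0.050 when always adjusting. An open choice among several covariates was not examined.

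**Capping.** Primary Outcome 1 is capped at 100%. The check was repeated with a latent normal clipped to 0–100, calibrated to control mean 75 and SD 20 and intervention mean 84 (where the SD falls to 17.1). Latent r = 0.3/0.5/0.7:

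- never adjusted: 0.757 / 0.757 / 0.755
- p<0.05 screen: 0.759 / 0.765 / 0.770
- cut-off 0.1: 0.783 / 0.842 / 0.931
- always adjusted: 0.786 / 0.850 / 0.946

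The pattern is the same; the gain at r = 0.5 is 9.3 points rather than 11.6.

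**The case against.** **The size is not pinned down.** Neither the screen nor r is in the documents. Against always adjusting, the loss runs from 0.4 power points (r = 0.3, cut-off 0.1) to 22.4 (r = 0.7, p<0.05). The protocol expects early salience to fade, which could weaken the link between the baseline month and months 4–9. At r = 0.3 full adjustment adds only 3.6 points, or 2.9 with capping. This stands as a limit on size. It does not rescue the rule: fixed adjustment had the highest power in every cell examined.

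**The mixed model may already use the baseline.** The schedule figure appears to mark MEMS adherence at allocation. If baseline days entered as responses with a common baseline mean, precision would be close to that of ANCOVA. That is a legitimate alternative, but the plan does not state it. The losses above apply to the static comparison of means.

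**An on-time baseline could serve Outcomes 3–4.** Assignment is revealed only after the baseline survey, so the control-arm wording on anchor timing may simply be loose, and an on-time share could be computed afterwards. No calculation shows mean adherence to be the better covariate for these outcomes. It is nevertheless a valid pre-intervention covariate, available in every arm without settling that question.

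**It is a pilot.** Feasibility and acceptability are central aims, power is disclaimed, age and sex are already committed, and the analyst is blinded. These points lower the stakes. They give no reason to discard information already collected.

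**Conclusion.** The concern holds. The rule ties adjustment to chance imbalance through an unnamed screen, and the baseline MEMS month has no stated place in any model for Primary Outcomes 1–4. If baseline adherence counts as a participant characteristic, it still enters only when imbalanced. If the ANCOVA does not cover the primary outcomes, their comparison has no stated adjustment beyond age and sex.

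The consequence is lost precision, not a false-positive problem. For mean adherence the available gain is roughly 4, 12 and 24 power points at r = 0.3, 0.5 and 0.7, and the unnamed screen decides whether about a tenth or most of it is lost. These sizes rest on the assumed r, alpha 0.05 and the plan's SD of 20. They cover Outcomes 1–2 only, because no SD is given for Outcomes 3–4. The change should be made; confidence in the size is medium.

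**What to change.** State in Statistical Methods and Analyses:

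> For Primary Outcomes 1–4, the ANCOVA and the linear mixed model will adjust for baseline-month mean MEMS adherence, age and sex, regardless of observed imbalance. Baseline-month days will not also be included as responses in the mixed model.

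The last sentence prevents the baseline being used twice.

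- **Outcome labels.** Correct them so that the ANCOVA sentence names Primary Outcomes 1–4.
- **Outcomes 3–4.** Use baseline mean adherence here too, rather than a baseline on-time share. Control Group: Usual Care says "At recruitment, participant will be educated about the importance of pill-taking using a leaflet" and then describes the anchor choice, whereas the Messages section places that choice when assignment is revealed. An on-time share may therefore not be defined alike across arms. The two sections must be reconciled.
- **Imbalance-driven adjustment.** Keep it only as a sensitivity analysis, with the screen and candidate list named.

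The cost is analysis wording and one to three degrees of freedom; no new data are needed. The Results section reports data collection complete and analyses ongoing, so the change is late. It must be dated and documented as made while the analyst is still blinded, which the documents alone cannot confirm. If r is near 0.3 the return is only about 3 to 4 power points.
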